All queries for this protocol should be sent to the IU project team using the ATN Protocol Query and Notification System (QNS) accessible via the ATN website (<https://www2.cscc.unc.edu/atn/>). [name] or the Consent 2.0 Program Manager will respond to queries generally within 48 business hours via the ATN QNS and copy the other team members. The Consent 2.0 Program Manager, with the help of other study staff and/or NICHD, if necessary, will answer general protocol implementation, eligibility, and data collection queries. The Protocol Chair or her designee will respond to study and participant management, exemptions and/or adverse event queries. Queries and replies will automatically be archived at the ATN CC. The Consent 2.0 Program Manager will post those queries deemed relevant to all sites on the ATN website, where they will be available for future reference.

This study will use Qualtrics to collect study data via the internet. All questions related to the Qualtrics survey and screening survey should be directed to the IU Data Manager ([name], [contact]) and the Consent 2.0 Program Manager ([name], [contact]) during regular business hours, Monday-Friday 8:00am-4:00pm ET. After hours Qualtrics questions should be directed to [name] at [contact]. Qualtrics questions/issues that do not require immediate attention should be sent via the ATN QNS.

For protocol or site registration issues or general ATN-related questions, contact [contact]. This account will be monitored on a regular basis during normal business hours.

LIST OF ABBREVIATIONS AND DEFINITION OF TERMS

AIDS	Acquired Immunodeficiency Syndrome
AMTU	Adolescent Medicine Trials Unit
ANOVA	Analysis of variance
ATN	Adolescent Medicine Trials Network for HIV/AIDS Interventions
CASI	Computer Assisted Self-Interview
CC	Coordinating Center
CFR	Code of Federal Regulations
CRF	Case Report Form
CO	Colorado
DHHS	U.S. Department of Health and Human Services
EC	Ethics Committee
eCRF	Electronic CRF
FDA	U.S. Food and Drug Administration
FIMSA	Federal Information Security Modernization Act
FIPS	Federal Information Processing Standards
FL	Florida
HIPAA	Health Insurance Portability and Accountability Act
HIV	Human Immunodeficiency Virus
HPTN	HIV Prevention Trials Network
ICH	International Conference on Harmonization
ID	Identification
IL	Illinois
IRB	Institutional Review Board
IT	Information Technology
IU	Indiana University
LGBTQ	Lesbian, gay, bisexual, transgender, questioning
MD	Maryland
MTN	Microbicide Trials Network
NICHD	National Institute of Child Health and Development
NIDA	National Institute on Drug Abuse
NIMH	National Institutes of Mental Health
NIST	National Institute of Standards and Technology
OHRP	Office of Human Research Protection
PAMAB	Pediatric, Adolescent, and Maternal AIDS Branch
PGP	Pretty Good Privacy
PI	Principal Investigator
PrEP	Pre-exposure prophylaxis
QA	Quality Assurance

QNS	Query and Notification System
RS	Research Staff
SID	Study Identification Number
SIS	Study Information Sheet
SMC	Study Monitoring Committee
STI	Sexually transmitted infection
STRC	Study Team Review Committee
TDF-FTC	tenofovir-emtricitabine
UBACC	UCSD Brief Assessment of Capacity to Consent
UCSD	University of San Diego
UE	Untoward Event
US	United States
WTP	Willingness to Participate
WTS	Willingness to Support
YMSM	Young men who have sex with men
YWSM	Young women who have sex with men

STUDY ABSTRACT

DESIGN:

This study will use CASI completed by all participants and a detailed debriefing interview completed for a subset of participants to assess high-risk minor adolescents' willingness to participate in and parents willingness to support their teen's participation in two hypothetical trials using simulated consent processes. The two hypothetical trials are modeled after ATN 113 and HPTN 077.

The purpose of this study is to examine how the consent process affects the acceptability of participation in biomedical HIV prevention trials, from the perspective of behaviorally high-risk minors and the parents of minor adolescents.

DURATION:

Study participation will last approximately 60 minutes on a single day with no follow-up. Participants who agree to participate in the debriefing interview will require an additional 45 minutes immediately following the completion of the main study procedures.

SAMPLE SIZE :

Approximately 144 (36 per study site) high-risk minor adolescents and 144 (36 per study site) parents of adolescents will be recruited for participation in this study. Of note, the adolescents and parents will not be parent-child dyads; they will be unrelated. A subset of 24-32 (6-8 per study site) adolescents and 24-32 (6-8 per study site) parents will be selected to participate in the debriefing interview.

POPULATION:

This study will recruit adolescents between ages 14-17, inclusive, who are able to read and speak English, who have a negative or unknown HIV status; and who have engaged in high-risk sexual activity in the last 12 months.

The study will also recruit adults who are able to read and speak English and who are parent or guardian to an adolescent who is between ages 14-17, inclusive.

Adolescents and parents will be recruited from four U.S. cities: Baltimore, MD; Chicago, IL; Denver, CO; and, Tampa, FL. These cities have diverse populations, high rates of incident HIV infection among adolescents and young adults, and/or demonstrated success in recruiting minor adolescents for biomedical HIV research.

RANDOMIZATION:

Adolescents will be randomized in a 1:1:1 ratio into 1 of the 3 consent conditions using block randomization with block size k=3 (so that in every 3 subjects, exactly 1 is allocated to each condition). The randomization will be stratified by study site and sex assigned at birth. Within study site, sex assigned at birth, and consent condition, the order in which the hypothetical trials will be presented to adolescents will be block randomized with block size k=2. A subset of 6-8 adolescents (3-4 males and 3-4 females) at each site will be selected for participation in the debriefing interview.

Enrollment of parents will be restricted to approximately 15 parents of adolescent natal males and 15 parents of natal adolescent females at each study site. Parents will indicate the acceptability of each of the three consent conditions for each of the two hypothetical trials. Independently of the gender strata, the order of hypothetical trial presentation will be block randomized with block size k=2. Separately for each hypothetical trial, the order of evaluation of the three consent conditions will be randomized so that each ordering is equally likely. A subset of 6-8 parents at each site (for total of 24-32) will be selected for participation in the debriefing interview.

SPECIFIC AIMS:

1. Describe how consent conditions influence high-risk minor adolescents' WTP in a hypothetical biomedical HIV prevention trial.
2. Describe how consent conditions affect parents' WTS a hypothetical biomedical HIV prevention study.
3. Describe the effects of the study agent (stage of development and method of delivery) on high-risk minor adolescents' WTP and parents' WTS a hypothetical biomedical HIV prevention trial.

STUDY PROCEDURES

Potential participants will be recruited from clinical settings and HIV testing centers, or self-screen online. Potential participants will take a short CASI screening survey to determine eligibility. All eligible participants will provide contact information to establish a study visit appointment. Those eligible and screening in-person will either participate on the same day as the screening, or, if unable to stay, they will be contacted to establish a study visit appointment. Eligible participants who screen online will also provide their contact information to establish a study visit appointment.

Study participants will attend an in-person session at their respective AMTU. During the session, they will complete a CASI that collects demographic, social, behavioral, and attitudinal measures.

All study participants will undergo a simulated consent process for each of two hypothetical studies modeled after ATN 113 and HPTN 077. Procedures are slightly different for parents than for adolescents, so each group is described separately below:

Adolescent Participants: First, the adolescent participant will complete a demographic CASI. *For each hypothetical trial*, RS will lead the participant through a simulated consent process consistent with their randomized consent condition. Then, the participant will complete a CASI assessing WTP and will work with RS to complete the UCSD Brief Assessment of Capacity to Consent (UBACC). After the second UBACC, the adolescent will complete overall WTP, medical mistrust, and end of study questions.

Parent Participants: *For each hypothetical trial*, RS will review the informed consent forms with the parent. The parent will complete a CASI with three vignettes that describe each of the three possible consent conditions. Parents will rate the acceptability of each vignette. Then, the participant will work with RS to complete the UCSD Brief Assessment of Capacity to Consent (UBACC). After the second UBACC, the participant will answer demographic questions, medical mistrust, and end of study questions.

A subset of 6-8 adolescents and 6-8 parents per study site will complete a debriefing interview assessing adolescent and parent perspectives on the various consent conditions in greater depth, and to better understand the role of study features, family, and adolescent characteristics in willingness to

participate/willingness to support the hypothetical research studies.

MONITORING:

Routine team monitoring of any adverse impact of the study will rely on the ATN Query & Notification System (QNS), a real-time, web-based interactive reporting system. Sites will record and enter in the ATN QNS, all untoward events associated with study participation, which will be reviewed on the Study Team Review Committee's monitoring calls. Routine team monitoring of protocol deviations will occur through Qualtrics. RS will enter any deviations into the Protocol Deviations Survey, which will automatically notify the central IRB site PI, [name], and her study team.

STUDY SCHEMAS

[figure not shown]

Figure 1A. Study schema, adolescent participants

[figure not shown]

Figure 1B. Study schema, parent participants

Legend for both figures:

- CC – Consent Condition
- CC 1: Adolescent self-consent
- CC 2: Adult permission required
- CC 3: Parental permission required
- CAB – Cabotegravir (an HIV treatment medication)
- CASI – Computer assisted self-interview
- RS- Research Staff
- WTP – Willingness to participate in the study
- UBACC – UCSD Brief Assessment of Capacity of Consent

1.0 INTRODUCTION

1.1 Background

American youth are disproportionately affected by the HIV epidemic, accounting for an estimated 26% of all new HIV infections. Young men who have sex with men (YMSM), and young women of color are at especially high risk. Together these two groups comprise 86% of all incident infections among persons aged 13-24.¹ New biomedical prevention approaches have dramatically decreased the risk of HIV infection in adults. One particularly promising approach is pre-exposure prophylaxis (PrEP), which involves prescribing an HIV treatment medication to those at high-risk of acquiring HIV. PrEP with once daily dosing of oral tenofovir-emtricitabine [TDF-FTC] has demonstrated 95% efficacy in adherent adult users.^{2, 3} The U.S. Food and Drug Administration has approved oral PrEP with TDF-FTC for adults aged 18 and older. There are currently no published data on the safety and efficacy of PrEP with TDF-FTC for minor adolescents, so it is not yet approved for prevention in this population.

One reason for the evidence gap is a well-described reluctance to include minors in biomedical HIV prevention research, because doing so presents ethical complexities.^{4, 5} There are three basic ethical principles that govern research with human subjects: respect for persons, beneficence, and justice.⁶ The first of these principles is the most difficult to operationalize in research with minors. Respect for persons requires treating individuals as autonomous actors, and protecting those with diminished autonomy. For decades, individual autonomy has been marked by attaining the legal age of consent to medical treatment or procedures,⁷ which is generally the age of majority, unless the treatment is for a socially stigmatized condition. Thus, in most research, minor adolescents fall into the category of those with diminished autonomy who require additional protection beyond those afforded to all human subjects. Parental permission is a cornerstone of these additional protections for minor research subjects.⁸ The requirement for parental permission is founded on several assumptions. The first is that children lack the capacity to understand and weigh the risks and benefits of research, and may make decisions that are not in their own best interest. The second assumption is that parents have a fundamental right to make decisions about their children's health and welfare, and to have those decisions reflect their own values. The third assumption is that parents will act in the best interest of their children.⁸

Connection to parents is often protective against a variety of risk behaviors,⁹ and disclosure to parents has been shown to be associated with a lower risk of HIV acquisition among YMSM.¹⁰ However, requiring parental permission forces the disclosure of sexual behavior, and in many cases, sexual orientation. Research demonstrates that requiring parental permission can delay treatment of stigmatized conditions, such as addiction, pregnancy, and sexually transmitted infections (STI) when adolescents fear social harms due to their disclosure to parents.¹¹ Delays in seeking treatment pose risk to the minor and, in some cases, to the public.⁸ Thus, for decades states have allowed minors to consent to the diagnosis and treatment of STI,¹² and, because of the way "children" are defined, these exemptions extend to research. Federal regulations allow minors to consent, without parental permission, to research that involves the same treatments or procedures to which they are allowed to self-consent in the jurisdiction in which the proposed research will take place.⁸ The allowance for minor self-consent is aligned with a body

of evidence that suggests adolescents are capable of making medical decisions that are comparable to the decisions of adults.¹³ It is also reflective of the findings of two studies^{14,15} in which the institutional review boards (IRBs) changed consent processes midway through, creating a natural experiment of the recruitment effect of requiring parental consent. In both of the studies it was found that self-selection bias toward lower-risk adolescents once parental consent was required for participation.

Investigators and IRBs must balance protective duties to minors with multiple vulnerabilities.¹⁶ Two PrEP studies^{17,18} have faced these ethical complexities directly, and each generated new questions that must be answered to make progress toward providing minors' appropriate access to HIV prevention research. The first study, ATN 113, examined the safety and tolerability of oral TDF-FTC for minor YMSM. Concerns about disclosure-related vulnerabilities prompted study organizers to design the protocol to allow for adolescent self-consent so that parental permission was neither sought nor required for enrollment. ATN 113 was the first biomedical HIV prevention study in the U.S. that allowed minor adolescents to self-consent for enrollment however roughly half the study sites failed to secure IRB approval for protocol implementation.¹⁹ The second study (MTN 023) is an active Phase IIa trial to assess the safety of a silicone vaginal ring impregnated with the antiviral dapivirine in adolescent women aged 15-17. Unlike ATN 113, MTN 023 study participants are required to have parental permission for enrollment. The study is underway, but investigators have encountered difficulty accruing participants within the planned timeframe for enrollment, raising concerns about the recruitment effects of requiring parental consent. Thus, neither of the two models of consent (adolescent self-consent or required parental permission with adolescent assent) facilitates adolescent inclusion in biomedical prevention trials. The first raises concern about exposure of the adolescent to harm; the second fails to attract adequate numbers because of the high risk for disclosure. Both raise important questions about the role of potential disclosure-related harms, participant gender, and study agent (delivery mechanism and stage of development) in shaping the consent process.

1.2 Rationale

This study will test a new model of consent for biomedical HIV prevention studies - optional parental permission. Consent has typically focused on a single actor--parent giving permission, or adolescent consenting for self. However, we will test a third model that includes the possibility of multiple actors. This support for a model of optional parental consent comes from a Phase III vaginal microbicide trial in South Africa.²⁰ Schenk et al. recruited 16-17 year-old girls and allowed them to self-consent for enrollment with the option to involve their parents if desired. The researchers were able to enroll and retain minors at very high risk of HIV, and found no differences in their attrition, adherence, or risk behaviors compared to 18-19-year-old study participants. These findings suggest that not only can minors participate in biomedical prevention studies but they can also be enrolled in a developmentally sensitive way. We want to determine whether a similar consent model would acceptable to high-risk adolescents and parents of high-risk adolescents in the US.

1.3 Preliminary Studies

Adolescents' capacity to consent to biomedical HIV research is roughly similar to that of adults. Ott has examined adolescent capacity to consent to research, and demonstrated that adolescents' capacity to understand consent information, to appreciate their own situation, the ability to balance risks and benefits, and to make a voluntary choice was similar to studies of adults.²¹ These data are similar to that of Hein, et. al.²² Through the Adolescent Medicine Trials Network ATN) for HIV/AIDS Interventions, Ott and Zimet examined preventive misconception with a simulated HIV vaccine trial. In that study (ATN 076), adolescents demonstrated the capacity to understand that the vaccine was an experiment (and thus may not work) and that a placebo would be used. Similar to adult studies and consistent with poor numeracy in U.S. populations, a higher number had difficulty understanding the statistical concept of randomization.²³

Lewis-Gilbert, Knopf, Zimet, et al. evaluated the process of initiating ATN 113 across the 13 sites that intended to participate in the study. The study raised numerous ethical challenges that primarily revolved around the principle of respect for persons. Investigators and IRB members expressed concerns about adolescent vulnerability that were not resolved even when there was a legal basis for adolescent self-consent.¹⁹ We also found that investigators and IRB members wished for an optional parental consent model, noting that some adolescents would want parental involvement in the consent process and some would not.²⁴ These studies point toward the acceptability of an optional parental consent model from the perspective of investigators and IRBs. The current study will elicit adolescent and parent perspectives.

2.0 SPECIFIC AIMS

The purpose of this study is to examine how the consent process affects the acceptability of participation in biomedical HIV prevention trials, from the perspective of behaviorally high-risk minors and the parents of minor adolescents. Acceptability will be measured by adolescents' willingness to participate (WTP) in and parents' willingness to support (WTS) their adolescent's participation in two hypothetical biomedical HIV prevention trials that are modeled after PrEP studies that included minors.

Aim 1: Describe how consent conditions influence high-risk minor adolescents' WTP in a hypothetical biomedical HIV prevention trial.

Primary Hypothesis: Adolescents assigned to the self-consent model will have the highest WTP scores, followed by those assigned to the adult permission model, and finally those assigned to the required parent permission consent model.

Additional sub-aims:

- Determine whether concern about HIV, capacity to consent, family context and sociodemographic characteristics moderate the relationship between consent condition and WTP scores.
- Describe high-risk minors' perceptions of the risks and benefits of parental consent, how they anticipate the different models of consent would influence their WTP in prevention trials, and whether shared-decision making between minors and parents is feasible.

Aim 2: Describe the acceptability of different consent conditions, from the parent perspective.

Primary Hypothesis: The parental permission required scenario will be the most acceptable to parents, followed by the adult permission model, and finally the adolescent self-consent model.

Additional sub-aims:

- Determine whether concern about HIV, capacity to consent, and sociodemographic characteristics moderate the relationship between consent condition and acceptability.
- Describe parents' attitudes toward the various consent models, their perceptions of the risks and benefits of each model, and their conceptualization of a shared decision making process for consent.

Aim 3: Describe the effects of the study agent (stage of development and method of delivery) on high-risk minor adolescents' WTP scores and parents' acceptability scores

Primary Hypothesis: WTP and acceptability scores will be higher for the study of an oral medication that is already FDA-approved for adults compared to study of a topical agent that is still under investigation.

Additional sub-aims:

- Describe perceived risks and benefits of each study design, and how adolescents and parents anticipate the study design would influence their WTP/WTS the hypothetical trial.

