10.3 Sample Size and Power Estimates

This study is powered to detect a meaningful difference in adolescent WTP scores and to detect a meaningful difference in parental WTS scores between the three consent conditions being studied. The WTP scores will be estimated as the mean score of three 5-point Likert scales. Based on the assumption that adolescent WTP scores are normally distributed and analyses using a linear regression model based on 120 participants (40 per consent condition) and with 7 independent variables in the model will provide 80% power to detect a $0.09 f^2$ effect size, which is between a small ($f^2=0.02$) and a medium effect size ($f^2=0.15$), for consent conditions. This power calculation, which assumed a single observation per participant, is conservative and the actual study which will have two observations per participant (one for each simulated consent process) will have a larger statistical power to detect an $f^2=0.09$ effect size for consent condition. Since the test of consent condition effects based on parental WTS scores is a within-participant comparison rather than an across-participant comparison, a test of parental consent condition effects will have 80% power to detect an even smaller effect size (f^2) compared to tests for consent condition effects using adolescent WTP scores.

A subset of 24–32 (6–8 per study site) adolescents and 24–32 (6–8 per study site) parent participants will be selected to participate in the debriefing interview. Prior research with similar populations suggest that this sample size is sufficient for eliciting a variety of perspectives and establishing key themes in the data.

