10.4 Statistical Analysis Plan

10.4.1 Quantitative Data Analysis

The primary analyses will estimate the effect of the three conditions and two hypothetical trial types on adolescent WTP scores and parent WTS scores. All analyses will be performed separately for adolescents and parents. The type I error rate will be set to $\alpha = 0.05$ separately for adolescent-specific and parent-specific hypothesis tests.

Linear mixed models will be used to estimate the effect of the three consent conditions and two trial types on WTP and WTS scores, with a random participant effect (i.e. random intercept) to account for the potential correlation between the multiple responses per participant. Aside from consent condition and trial type effects, the LMMs will also include adolescent's sex assigned at birth and study site as fixed effects.

Heterogeneity of consent condition and trial type effects across study sites will be evaluated. If statistically significant interactions occur ($p<0.05$), site-specific estimates of effects will be presented to supplement the pre-planned analyses. P-values from pairwise comparisons of consent condition effects will be adjusted for multiple comparisons to control the type I error rate at the level $\alpha=0.05$ separately for parents and adolescents. Tests of trial type effects will be performed at the level $\alpha=0.05$ separately for adolescents and parents and separately from tests of consent condition effects.

As a secondary sensitivity analysis, we will evaluate whether concern about HIV, family context (frequency of communication, connectedness), and other demographic and socioeconomic factors affect WTP/WTS participation in biomedical research. We will examine these effects by adding variables into the models to determine if they moderate the relationship between consent condition and WTP/WTS scores.

Although WTS and WTP scores are discrete, it is common to analyze these data using linear models. Research suggests that this approach is robust to the discrete nature of the data if the normality assumption is not severely violated. However, usage of the LMM may be problematic if a large number of responses occur on the boundary (e.g. a high proportion of 1's or 5's). In this case we will fit a linear quantile mixed model for the median WTP and WTS scores, which does not require normality.³⁴

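### The 80% power in 10.3 is for any difference between consent conditions; it does not extend to the Aim 1 ordering, and 10.4.1 names neither an adjustment method nor a rule for that ordering

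*Combined protocol and SAP*

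**What the plan says.** Section 2.0 words the aim descriptively: "Aim 1: Describe how consent conditions influence high-risk minor adolescents' WTP in a hypothetical biomedical HIV prevention trial". Beneath it stands a primary hypothesis that ranks all three conditions: "Adolescents assigned to the self-consent model will have the highest WTP scores, followed by those assigned to the adult permission model", and required parental permission last.

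Section 10.3 states the power objective as a difference, not a ranking: "This study is powered to detect a meaningful difference in adolescent WTP scores" between the three conditions. The calculation is "based on 120 participants (40 per consent condition) and with 7 independent variables in the model", and it "will provide 80% power to detect a $0.09 f^2$ effect size" for consent conditions. The section adds: "This power calculation, which assumed a single observation per participant, is conservative", because each adolescent gives two ratings. Section 3.2 plans about 144 adolescents, which is 48 per condition at 1:1:1.

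Section 10.4.1 fits a linear mixed model to estimate the consent-condition effects, with alpha 0.05 for adolescents. On comparisons between conditions it says: "P-values from pairwise comparisons of consent condition effects will be adjusted for multiple comparisons". It names no adjustment method and no overall test, and it does not say which result would support the ordering.

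**The concern.** An overall test can reject without showing where the middle condition lies. The hypothesis is about that position: adult permission should fall below self-consent and above parental permission. Each of those two gaps is only part of the total spread, so each is harder to detect than a difference somewhere among the three.

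The middle condition matters. Section 1.2 presents a model with optional parental involvement as the new one to be tested, and the adult-permission condition is its counterpart here. A reader who sees a primary hypothesis and a single power figure may carry the 80% over to the ordering. The likely result under a true ordering is that the extremes differ and the middle condition is not separated from at least one neighbour. With no stated rule, that result could be reported as support or as failure.

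**Working it through.** **Inputs from the documents.** N = 120 (40 per condition), 7 independent variables, f² = 0.09 for consent condition, one observation each (10.3); alpha 0.05 (10.4.1); 144 planned, so 144/3 = 48 per condition (3.2, 3.3); two ratings per adolescent (3.4.1).

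**Assumptions not in the documents.** Equally spaced means; two-sided pairwise tests; f² on the single-rating scale; within-person correlation ρ of 0.3–0.8.

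**1. Reproduce the 80%.** Three conditions give u = 2. Error df v = 120 − 7 − 1 = 112. With noncentrality λ = f²(u + v + 1) = 0.09 × 115 = 10.35, the noncentral F gives 81.8%. With λ = f² × N = 10.8 it gives 83.5%. Under the first convention the f² for exactly 80% is 0.086, which rounds to 0.09. A 1-df test would give 89–90% and a 7-df test 62%, so the stated figure fits the overall 2-df test and no other.

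**2. Turn f² into differences.** For means d, 0, −d in residual SD units, the between-condition variance is (2/3)d². Setting this to 0.09 gives d = √0.135 = 0.367. Adjacent steps are therefore 0.367 SD and the extremes are 0.735 SD apart.

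**3. One adjacent step by hand.** The standard error at 40 per condition is √(2/40) = 0.2236, so the expected t is 0.367/0.2236 = 1.64. The Bonferroni critical value (0.05/3, 112 df) is about 2.43, so power is about Φ(1.64 − 2.43) = Φ(−0.79), or 21–22%. Simulation gives 22%. For the extremes the expected t is 3.29, and Φ(3.29 − 2.43) = Φ(0.86), about 80%.

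**4. Simulated power** (at least 300,000 trials per setting, pooled error). Two ratings are modelled by multiplying the variance by (1 + ρ)/2, so the effective f² is 0.09 × 2/(1 + ρ): 0.100 at ρ = 0.8 and 0.138 at ρ = 0.3. "Gated" in the table's sense means the three pairwise tests at unadjusted 0.05, run only if the overall F test is significant.

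| Setting | Method | Each adjacent step | Both steps | Extremes |
|---|---|---|---|---|
| 40 per condition, one rating | Tukey | 24% | 1.7% | 82% |
| | Holm | 28% | 5.9% | 81% |
| | Gated | 36% | 6.9% | 83% |
| 48, one rating | Tukey | 29% | 3.2% | 89% |
| | Holm | 35% | 9.8% | 88% |
| | Gated | 43% | 11% | 90% |
| 48, two ratings, ρ = 0.8 | Tukey | 32% | 4.6% | 92% |
| | Holm | 39% | 13% | 92% |
| | Gated | 47% | 14% | 93% |
| 48, two ratings, ρ = 0.3 | Tukey | 45% | 12% | 98% |
| | Holm | 55% | 27% | 98% |
| | Gated | 60% | 29% | 98% |

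**5. Uneven spacing.** With a 2:1 split of the same f² at 40 per condition, Tukey gives 42% and 10% for the two steps and 1.3% for both. Unequal steps do not rescue the joint figure.

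**6. Error control of the gated procedure.** With three groups, if any two pairwise nulls are true then all three means are equal. The overall null is therefore the only intersection that a closed test must cover. In simulation the familywise error is 0.050 with all means equal, and 0.050 with two equal and the third far away.

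**The case against.** Three points on the other side are sound.

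First, a reader might infer that the 80% is a miscalculation. It is not. It reproduces, and 10.3 describes it as power for a difference between the conditions. The section nowhere claims power for the ordering.

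Second, a reader might infer that 10.4.1 decides the ordering by adjusted pairwise tests, so that the study has about a 2% chance of confirming its hypothesis. The documents do not support that. Section 10.4.1 says only that pairwise p-values will be adjusted, and requiring both adjacent steps to be significant is the strictest reading of an aim worded as description. The 2% also needs Tukey, equal spacing, 40 per condition and one rating. The first two are not in the documents, and the last two are less favourable than the planned design.

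Third, it would be too strong to say that the trial will nearly always be silent about the middle condition. Under equal spacing, at least one adjacent step is significant in 46% (Tukey) to 50% (Holm) of trials at 40 per condition. The estimated means fall in the hypothesised order in 90% of trials there, and in 94–97% under the planned design with ρ of 0.3–0.8.

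What stands against all three is that the overall-test power does not carry over. No pairwise power, adjustment method or rule for the ordering is given, and power for both steps is below 30% in every setting tried.

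**Conclusion.** The point holds as a gap in specification and in how the power is described, not as an arithmetic error. The 80% applies to an overall 2-df difference. At the same f² with equal spacing, power to separate the middle condition from one neighbour is about 24–28% at the inputs of 10.3, and about 32–55% under the planned design with ρ of 0.3–0.8 (Tukey to Holm). Power for both steps is about 2–6% and 4.6–27% respectively. Self-consent versus parental permission has at least about 80% in all of these settings, so the contrast between the extremes is adequately powered.

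It might also be inferred that a 1-df linear contrast would settle the ordering, since it has about 90% power at 40 per condition and 95% at 48 with one rating. With three equal groups its weights are (1, 0, −1). It is the unadjusted test of the extremes and gives the middle condition no weight. If the middle mean equals the top one at the same f², it still rejects about 81% of the time although the strict ordering is false.

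These figures are for adolescents. Parents rate all three conditions, so their comparisons are within-person and were not recomputed.

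**What to change.** 1. In 10.4.1, replace the unnamed adjustment. Test the overall 2-df consent-condition effect at 0.05 and, only if it is significant, run the three pairwise tests at unadjusted 0.05. Adjacent-step power rises from 24% (Tukey) or 28% (Holm) to 36% at 40 per condition, and from 29% or 35% to 43% at 48, both with one rating. The same closed-test argument can be used separately for parents.
2. In 10.3, label the 80% as power for the overall 2-df test. State that power to separate the middle condition from a neighbour, or to establish the full ordering, is much lower, and give the range with its assumptions.
3. State the rule: claim the full ordering only if both adjacent differences are significant in the hypothesised direction; otherwise report the estimated order descriptively. Do not present a linear contrast as evidence about the middle condition.

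The cost is SAP wording, with no added participants or data. Pairwise confidence intervals would no longer be simultaneous, and the stated prospects for ranking the middle condition become less favourable. The gated tests do not cure the low joint power: both steps reach only about 7% at 40 per condition with one rating and 14–29% under the planned design, which is why item 2 is needed as well.
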